6.1. Sample Size

A feasibility count conducted in November 2024 identified 96,125 visits with information in ISAR from May 2017. Of these, the provision of data to the central site was through the ISAR electronic data case report form for 81,396 (85%) patients, whereas data on 20,293 (15%) patients was sent through bespoke methods. Around one quarter of visits were KPR (either new patients or switches/new biologic treatments) and three-quarters were RR (follow-up visits).

ISAR feasibility count: 26 November 2024			
Total number of patients		96,125	100%
Data transfer method	Bespoke	14,728	15%
	Electronic data capture	81,397	85%
Visit type	New patient visits	20,293	21%
	Switch/New biologic	3,036	3%
	Re-review	72,796	76%

6.2. Software

[figure not shown]
This project will use Stata statistical software v15.1 (10), SQL Server Management Studio (v20) and joinpoint trend analysis software from the Surveillance Research Program Cancer Institute Version 5.30 (Division of Cancer Control & Population Sciences, National Cancer Institute, US): <https://surveillance.cancer.gov/joinpoint/> (11).

6.3. Statistical methods for each objective

For all objectives (apart from objective 4), trends in reporting (both longitudinally and using repeated cross-sectional analyses using historical data snapshots) will be partially investigated using joinpoint analysis. Joinpoint regression is a piecewise linear (or log-linear) regression to describe trends, changes in trends and specific change-points (or joinpoints) in relation to the characteristics of disease or another outcome over time. The joinpoint trend analysis software used starts with the minimum number of joinpoints (i.e. zero joinpoints – a straight line) and tests whether more joinpoints are statistically significant and need to be

added to the model. Up to three joinpoints will be investigated using a weighted Bayesian Information Criterion (BIC) test (recommended by the Joinpoint software for its optimal performance and sensitivity to small changes in trends) (13,14) and a parametric method. A significant difference from no change of each segment will be evaluated using a 5% level of probability ($p < 0.05$) using annual percentage changes (APC) to indicate fluctuations in trends across distinct intervals (14). See **Figure 1** for a sample joinpoint graph adapted from the graph shown on the National Cancer Institute website: <https://surveillance.cancer.gov/joinpoint/>.

Figure 1: Sample joinpoint analysis graph, showing 4 joinpoints

* Annual percentage change (APC) significantly different from zero at alpha 0.05

* Source: <https://surveillance.cancer.gov/joinpoint/>

The software used for the trend analyses identifies inflections in the data without pre-specified knowledge at which the time points are expected to occur. In some situations, this knowledge is important as we may wish to investigate whether improvements have occurred after the introduction of specific interventions, such as new data capture systems and/or change in response to latest research evidence, policy initiatives and QI initiatives. We also wish to evaluate whether the quality improvement plans for the ISAR introduced from 2023 (data quality report, country-specific data quality dashboard, face-to-face meetings on data quality

issues) had any impact on data quality. We will also explore the effects of the confounder COVID and adjust for this, if necessary. Therefore, we will investigate how trends differ before and after a given intervention using a single group interrupted time series analysis (ITSA) using calendar year as the time variable. This will involve creating a spline of year with a knot placed at either one or several intervention periods and creating a variable to partition time periods to before and after the given intervention. Where the key period differs for each country (e.g. introduction of QI initiatives as part of the ISAR), we will explore changes either side of the key period (set to be time zero). A linear mixed effects model will be used to assess the percentage of variables that are complete (objective 2) by intervention period and covariates, modelling variation in country as a random effect. The odds of LTOC use (objective 3) pre- and post-intervention period will use a logistic mixed effects model, also using a random intercept for each country. For both methods, 95% confidence intervals will be calculated using bootstrapping techniques. For the time-to-event components of objective 3 (i.e. time from LTOCS to stopping/reducing LTOCS) and objective 4 (i.e. time to initiating biologic by asthma severity indicator), we will use time-to-event analyses (both non-parametric and flexible parametric methods).

Objective 1: Proportion of patients in ISAR with 100% completeness of key research variables from 1 May 2017 to latest date available

We will use data from the ISAR registry from May 2017 to the latest date available to calculate the proportion of patients in each calendar year with 100% completeness of key research variables from 1 May 2017 to latest data available. Reviews will be stratified into KPRs and RRs, and method of provision for each country (i.e. ISAR-built electronic data capture vs bespoke). Joinpoint analysis will be used to identify each calendar year period (i.e. the predictor variable) at which there is a change in the proportion of patients reaching 100% completeness and the size of this change (percentage change in rate per calendar year). A log-linear model will be used to analyse percentage change in rate over time, reporting on the linear trend in each segment, also stratifying by country to explore country-specific effects. We will also investigate specific inflection points/periods during the observation period using ITSA.

Objective 2: Completeness of recording of all core variables in ISAR

Annual trends and changes in the proportion of core variables will be investigated in ISAR, also stratifying by country and provision of data method. The completeness of individual core variables will also be investigated to assess the variables that are least likely to be complete.

We will use a combination of joinpoint regression (to investigate trends) and ITSA (to investigate pre-specified inflection time points) with variation in country modelled as a random effect for this component of the analysis, also stratifying by data capture method. **Appendix 1** (Section 13.1) shows the complete list of core variables in ISAR.

Objective 3: Differences in the proportion of patients in ISAR who are prescribed LTOCS varies over time, and the characteristics of these patients

Trends in the proportion of patients with a LTOCS prescription in a given year (i.e. yes/no) and average dose of LTOCS will be described and plotted by calendar year using a combination of joinpoint regression and ITSA to analyse significant changes in trends, also stratifying by country-specific data capture method. For those on LTOCS, we will also investigate the probability of stopping/reducing LTOCS dose (<5mg) using time-to-event analysis (non-parametric [Kaplan-Meier] and flexible parametric methods). Patient characteristics for people with and without missing/incomplete data on LTOCS will also be compared.

Objective 4: Trends in the severity of asthma indicators in those initiating biologic treatment over time

The probability of initiating biologic treatments by asthma severity indicator and calendar year will be investigated using time-to-event analyses (non-parametric and flexible parametric models).

7. Regulatory and Ethical Compliance

This study was designed and shall be implemented and reported in accordance with the criteria of the “European Network Centres for Pharmacoepidemiology and Pharmacovigilance (ENCePP)” and follows the ENCePP Code of Conduct (EMA 2014). Once a final version of the protocol has been agreed and reviewed by the advisory group, this study will be registered with ENCePP (www.encepp.eu).

ISAR is approved by the Health Research Authority for clinical research use and governed by the Anonymised Data Ethics & Protocol Transparency (ADEPT) Committee. We will submit the finalised version of this protocol to the ADEPT committee (<https://www.regresearchnetwork.org/adept-committee/>) for approval.

All sites enter into a regulatory agreement in compliance with the specific data transfer laws and legislation pertaining to each country and its relevant ethical boards and organisations. Further, all data extracted from sites is de-identified in the form of anonymised patient IDs. The data will be retrieved by Optimal Patient Care/Observational & Pragmatic Research Institute data analysts and utilised as an anonymised dataset to perform the analysis according to protocol. This study will be performed in compliance with all applicable local and international laws and regulations, including without limitation ICH E6 guidelines for Good Clinical Practices.

8. Data Dissemination

This study is the first of its kind to formally investigate data quality improvements over time in ISAR. The assessment of clinical outcomes (objectives 2 and 3) over time will help to assure both data quality and patient outcomes.

Publications:

The findings will be submitted for publication in peer-reviewed journals that focus on data quality (Data, JAMIA Open; Objective 1) and respiratory diseases, biologic therapies, and clinical outcomes (Objectives 2 and 3).

Conferences:

Results will also be presented at relevant medical and scientific conferences, through abstract presentations and/or discussions.

Authorship:

Authorship will be determined in accordance with the ISAR authorship policy as outline in the ISAR publication charter, which has been approved by the ISAR steering committee. Authorship will recognise significant contributions to the study's conception, analysis, and writing.

9. Project management group and wider steering committee group

[name], Chief Investigator for the study, is the chair of the ISAR Steering Committee (ISC).

The project management group for this project will be led by [name]. Other members of the project management group are listed below.

No	Name	Country / Institution
1	[name]	Argentina
2	[name]	Argentina
3	[name]	Argentina
4	[name]	Argentina
5	[name]	AstraZeneca
6	[name]	AstraZeneca
7	[name]	AstraZeneca
8	[name]	AstraZeneca
9	[name]	AstraZeneca

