Healthcare registry data require robust quality improvement initiatives as they have the potential to provide a rich source of surveillance data on healthcare patterns, clinical decision making and delivery of interventions that can, ultimately, improve patient outcomes (3). However, registry data also rely heavily on understanding how the data were derived and why they were recorded so that its users can interpret the results meaningfully. For example, when using registry data that combine information on patients from different sites and countries, consideration needs to be made of relevant healthcare systems and specific national policy initiatives.

This study investigates the quality of the International Severe Asthma Register (ISAR) data over time and during key policy and quality improvement initiatives of a longitudinal, real-life data registry for patients with severe asthma (4). The ISAR provides a useful framework through which other quality improvement initiatives can be developed as it is underpinned by data quality goals that align with stakeholder needs and the needs of patients with severe asthma. Such goals include high level of completeness in the collection of core variables and key research variables, which help to inform both day-to-day clinical decision-making (e.g. by identifying patients, who may benefit from further monitoring or treatment), and promote severe asthma research (e.g. treatment efficacy/effectiveness). At the forefront of the ISAR initiative's original (and continuing) mission was to reduce long-term oral corticosteroid (LTOCS) exposure (5) and facilitate the provision of an international consortium for research collaboration in respiratory medicine and patient care (6). A minimum core set of variables for the ISAR was developed in 2017 as part of a modified Delphi process consisting of 3 iterative rounds and two face-to-face meetings with a panel of 27 international experts in the field of severe asthma research (7). A follow-on Delphi exercise was conducted in 2023 to identify key variables for use in research, which was further refined in 2024. Additional quality improvement plans for the ISAR were introduced from 2023. These included the introduction of a data quality report, a country-specific data quality dashboard, face-to-face meetings on

data quality issues, and (optional for some countries) an optimised electronic case report form (eCRF).

2. Study Aims and Objectives

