4.2. Inclusion and Exclusion Criteria

Inclusion Criteria

- Patient meets criteria for severe asthma:
 - On Global Initiative for Asthma (GINA 2021) Step 5 (8)
 - Uncontrolled on GINA Step 4, at least one of the following:

- poor symptom control: asthma control questionnaire ACQ>1.5, ACT<20 or "not well controlled" by National Education and Prevention Program [NAEPP]/GINA guidelines (8,9)
- airflow limitation: after appropriate bronchodilator withhold Forced expiratory volume in one second (FEV1) <80% predicted (in the face of reduced FEV1/forced vital capacity [FVC] defined as less than the lower limit of normal)
- serious exacerbations: at least one hospitalisation, intensive care unit (ICU) stay or mechanical ventilation in the previous year
- frequent exacerbations: two or more bursts of systemic corticosteroids (>3 days each) in the previous year

Exclusion Criteria

- For Objective (3), patients will be excluded if they have an unknown LTOCS status (objective 3 – although we will look at 'unknown' LTOCS that has been completed retrospectively to assess any potential for bias), if they have information on only 1 visit, and/or they are not taking LTOCS at their baseline visit (defined by first visit with LTOCS=yes). For Objective (4), patients will be excluded if they have unknown biologic status and/or none of the asthma severity indicators at baseline (defined by first visit with asthma severity indicator=yes)
- Patients (from some countries/regions) who have not consented for their data to be used for research purposes and/or data that have been approved for specific studies only.

5. Study Variables and Study Outcome Definitions

Objective 1: Proportion of patients on the ISAR with 100% completeness of key research variables from 2017 to latest date available

Outcome: Proportion of patients meeting 100% completeness of key research variables by patient status (i.e. new patients and follow-up visits)

Exposure: Time (calendar year and pre-specified periods of change)

Covariates: Country (numbers allowing), Country-specific factors (method of data provision, healthcare setting, date of participating in ISAR), visit-specific factors

We will focus on key research variables, as voted for in the 2023/24 Delphi exercise. For first visits or where patient starts or switches a biologic (**KPR visits**), 16 variables will be investigated (see **Table 1**). For **re-review (RR)** visits, 11 variables will be investigated.

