We will divide the visit dates into calendar years and assess the proportion of all individuals meeting the criteria for 90% and 100% key research variables to assess whether there are any changes/trends over time. We will also investigate before and after completeness over key periods (e.g. introduction of quality improvement initiatives [period from introduction of data quality [DQ] dashboards, reports and face-to-face meetings], changes in data capture systems) where we might expect completeness to change. As well as looking at changes by calendar year for the most recent complete data set, we will use snapshot data to assess completeness and accuracy of data in different snapshot periods. This process will allow for the evaluation of backdated quality improvements in the data. For example, 2021 data from 2024 will be compared with 2021 data captured in 2021, 2022 and 2023 (and different quarters within this period where we might expect to see changes).

Table 1. Key research variables as voted for in Delphi by key prior review (KPR) and re-review (RR) visits

KEY	KPR & RR	KPR ONLY	RR ONLY
-----	----------	----------	---------

Category	Variable Field Name	Key prior review	Re-review
DOV	Date of visit		
AGE, GENDER, HEIGHT & WEIGHT	Date of Birth		
	Gender		
	Weight		
	Height		
SMOKING STATUS	What is the current smoking status of the patient?		
ASTHMA ONSET	At what age did the patient's asthma symptoms begin? Whole years or months if < 1 year		
EXACERBATION	Number of exacerbations requiring rescue (systemic/oral) steroids in the past 12 months?		
HOSPITAL ADMISSION	Total number of hospital admissions for asthma in the past 12 months?		
CHRONIC RHINOSINUSITIS	Indication of: Chronic Rhinosinusitis		

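### Section 6.3 fixes calendar year as the time unit of the interrupted time series, which is too coarse to separate a step from a trend after quality measures introduced only from 2023

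*Protocol*

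**What the plan says.** Section 6.3 says that before/after differences around a given intervention will be studied "using a single group interrupted time series analysis (ITSA) using calendar year as the time variable". The construction has two parts. The first is the trend: "This will involve creating a spline of year with a knot placed at either one or several intervention periods". The second is a separate step of "creating a variable to partition time periods to before and after the given intervention".

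Staggered starts get their own sentence. It opens "Where the key period differs for each country (e.g. introduction of QI initiatives as part of the ISAR" and continues "we will explore changes either side of the key period (set to be time zero". No unit of time is restated there.

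On dates, section 1 says only this: "Additional quality improvement plans for the ISAR were introduced from 2023". Section 6.3 repeats the year. Neither gives a month.

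Section 5 defines the exposure, in the same words for each objective, as "Exposure: Time (calendar year and pre-specified periods of change". For Objective 1, section 6.3 makes the outcome a proportion per calendar year and then adds the interrupted time series, without saying whether that analysis runs on the annual proportions or on visits.

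A finer unit appears once, in section 5 under Objective 1, where snapshot comparisons may look at "different quarters within this period where we might expect to see changes".

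**The concern.** The QI measures are the main intervention the time series is meant to evaluate, and they sit at the very end of the observation window. Whole years then cause two difficulties.

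- **Too few points.** There are about two annual points from 2023 on, which leaves nothing to check a fitted post-QI level and slope against.
- **Mixed start year.** An annual point for a year in which a measure began part-way blends visits before and after the start.

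Either way, a one-off gain and a steadily growing gain become hard to tell apart, and that distinction is what the analysis is for. The study could report a small immediate effect with a rising trend when the truth was a single step. The same applies to any other mid-year change tested, such as a new data capture system.

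**Working it through.** The protocol states no effect size or precision for this analysis, so there is no figure of its own to reproduce. What follows is a noise-free illustration.

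**Inputs from the protocol**
- Time variable: calendar year (section 6.3).
- Observation starts 1 May 2017 (section 2.2).
- QI introduced from 2023, month not given (sections 1 and 6.3).

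**Assumptions**
- Data end November 2024, the month of the feasibility count in section 6.1.
- Visits are even across months.
- The truth is a pure step of 10 percentage points with no slope change.
- A fraction *f* of 2023 passes before the start.

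**1. Number of points.** May 2017 to November 2024 is 91 months in 8 calendar years: 6 before 2023 (2017 is partial) and 2 from 2023 on. A segmented model has four mean parameters: intercept, prior slope, level change and slope change. Two are set by the six earlier points and two by the last two points. The post-QI segment fits exactly, with 2 − 2 = 0 degrees of freedom.

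**2. Year-coded status, level plus slope.** Measured from the extrapolated pre-2023 line, whether flat or rising by a constant amount per year:
- expected excess in 2023 = 10(1 − *f*)
- expected excess in 2024 = 10
- fitted level change = 10(1 − *f*)
- fitted slope change = 10 − 10(1 − *f*) = 10*f*
- share of months from January 2023 to November 2024 that are really pre-QI = 12*f*/23

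| Start in 2023 | *f* | Level change | Slope change per year | Pre-QI share of post months |
|---|---|---|---|---|
| January | 0 | 10.0 | 0.0 | 0/23 = 0% |
| April | 0.25 | 7.5 | 2.5 | 3/23 = 13% |
| July | 0.50 | 5.0 | 5.0 | 6/23 = 26% |
| October | 0.75 | 2.5 | 7.5 | 9/23 = 39% |

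**3. Year-coded before/after indicator alone** (flat background). The estimate is 10(23 − 12*f*)/23, which gives 10.0, 8.7, 7.4 and 6.1 for the four starts.

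**4. Spline of year without a level term** (knot at 2022, flat background). The slope change is about 4.9 to 5.2 points per year for every start month, January included. Here the missing level term, not mid-year timing, turns the step into a slope.

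**5. Date-based coding.** Two visit-level models return a level change of 10.0 and a slope change of 0.0 for all four starts:
- a yearly trend with an indicator coded from the visit date
- monthly time centred on the actual start

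**6. If the data ran through all of 2025.** Three post points for a July 2023 start have excesses 5, 10 and 10 at times 0, 1 and 2. The slope is (10 − 5)/2 = 2.5 and the level is 25/3 − 2.5 = 5.8. A further year halves the spurious slope but does not remove it.

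**The case against.** A reader might infer that the plan certainly codes pre-QI visits as post-QI and so will misread a step as a trend. The protocol does not support that, for four reasons.

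- **Start month.** The measures are dated from 2023 with no month, and a January start misclassifies nothing.
- **Before/after variable.** It is described separately from the spline of year, and nothing says it is built from year rather than visit date. Coded by date and entered as a level term in a visit-level model, it recovers the whole step.
- **Staggered starts.** These are not ignored: each country's key period becomes time zero. Section 5 also lists event-defined periods alongside calendar year as exposure.
- **Left to the analysis plan.** How the indicator and time zero are derived is commonly settled in a statistical analysis plan, which is not shown here.

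All of this stands against the categorical reading. It does not answer three things.

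- The yearly unit is a choice the protocol makes, not a detail it omits.
- Setting time zero aligns countries but does not shorten the unit.
- If the Objective 1 series is the annual proportion itself, visits on either side of a mid-year start are already pooled, and no indicator can separate them.

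Two further cautions are fair. The mention of quarters in section 5 concerns when snapshots were captured, not a series by quarter of visit, so it does not show that the plan already intends a finer time variable. And section 3 says that sites correct data retrospectively, so visits dated before QI may have been completed after it. Date coding alone does not give a clean contrast in the current data set for Objectives 1 and 2.

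**Conclusion.** The point holds as a coarse, stated choice of time unit. If data end in late 2024, whole years leave about two points from 2023 on, and a level-plus-slope model is saturated after QI whatever the start month.

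Misclassification is a conditional risk. It needs a start within a year, and also before/after status or time zero set by year, or an outcome already aggregated by year. Under those conditions an assumed 10-point step loses 2.5 to 7.5 points of level for April to October starts, and the same amount reappears as slope change per year. With a January start the level-plus-slope fit is unbiased. The sizes scale with the assumed step and start date. They illustrate the mechanism and do not forecast this registry's bias.

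**What to change.** In section 6.3:

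- **Time unit.** Replace calendar year as the time variable of the interrupted time series with month or quarter of visit, or with months from each country's own start date. The last extends the time-zero approach already planned.
- **Level term.** State that the model has a level change as well as a slope change.
- **Coding.** State that before/after status follows the visit date compared with the actual start date of the measure in that country, and list those dates.
- **Objective 1.** Say that the series is built at this finer unit and not from annual proportions.
- **Snapshots.** For Objectives 1 and 2, run the before/after contrast on the historical snapshots as well, because of retrospective correction.
- **Keep calendar year** for descriptive plots and joinpoint analysis.

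The cost is wording, analysis code and a table of start dates. Date of visit is a key variable at both visit types (Table 1) and a core variable required at every visit (Appendix 1), so no new data are needed from sites. The downside is noisier points in small countries, where quarters may serve better than months, and a need for seasonal terms.
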